#### **Day 5 of Stimulation (Visit 9)**

The participant will be asked to decide if they would like to complete the clinical assessments over the phone or in person. If they prefer the phone/webex, the participant will be contacted before coming into the lab and the AHRS (*Attachment 3*) and PANSS (*Attachment 5*) will be administered. Upon participant arrival at the lab, vital signs will be taken and documented at the beginning of the first stimulation session of the day. An EEG will then be administered, with ECG data also being collected at this time. The EEG recording will include resting state data along with an auditory task, and the EEG Questionnaire will be administered. The participant will receive 40-minutes of sham or 10 Hz tACS (as per the initial randomization) while sitting quietly with their eyes open. The *Reefscape* video will be played during the stimulation session. Each stimulation session will be followed by the stimulation adverse effects questionnaire. The BACS (*Attachment 6*) data collection assessments will be administered at the end of this session. If the participant opted to complete the clinical assessments in person, the AHRS (*Attachment 3*) and the PANSS (*Attachment 5*) will be administered at the end of this session. After the assessments are completed, the participant will then be paid at the completion of the session, and the first maintenance session will be scheduled for the second week after their last day of stimulation (one gap week in between).

---

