## PROTOCOL SUMMARY

[figure not shown]
Title	STILL 3 Study
Brief Summary	
The purpose is to provide further evidence concerning the efficacy of tACS for treatment of auditory hallucinations and to evaluate an exploratory maintenance stimulation paradigm to prolong the duration of stimulation-induced clinical benefits. We will study 40 eligible males and females diagnosed with schizophrenia or schizo-affective disorder. The longitudinal experimental design is a two-treatment, 4-sequence, multi-period randomized crossover design. During the first week, the enrolled participants will have 5, daily, 40-minute stimulation sessions. At the end of the first week, the participants will begin an 8-week maintenance regimen of weekly 40-minute stimulation sessions.
 
A randomization protocol will be used to assign each participant to either a sham regimen or an active regimen during the first week, and to a sham or active maintenance regimen. Equal numbers of participants will be assigned by random allocation to the four treatment-sequence groups: tACS-tACS, tACS-sham, sham-tACS, sham-sham.
 
Participation will involve 1 to 18 visits. At the initial phone session, informed consent will be obtained and subjects will be screened for eligibility. Participants will be contacted again in 2 weeks for a second phone screening session to determine stability of auditory hallucination symptoms, utilizing the Auditory Hallucinations Rating Scale (AHRS, attachment 3). If the AHRS scores are within <math>\pm 20\%</math> of their previous score, they will be considered eligible. If the AHRS scores do not fall within this range, participants will be rescheduled for a third or fourth screening session separated by 2 weeks. If, after the fourth screening session the participant does not have stable AHRS scores, they will not be eligible to participate.
 
Eligible participants will be scheduled for their daily stimulation sessions which will include a daily assessment of stimulation side-effects. Clinical assessments of auditory hallucinations will be administered with the AHRS and the self-administered Hamilton Program for Schizophrenia Voices (HPSVQ). These measurements will be assessed at the time of enrollment into the study (baseline), at the first day of stimulation, at the fifth day of stimulation, and once weekly for 8 weeks of maintenance stimulation sessions. Neurophysiological (EEG) and cognitive assays will be performed day 1 of stimulation, day 5 of stimulation, and at maintenance stimulation sessions for weeks 1, 3 and 8. In conjunction with

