### **4 STUDY DESIGN AND OUTCOME MEASURES**

#### **4.1 STUDY OUTCOME MEASURES**

##### **4.1.1 PRIMARY OUTCOME MEASURES**

The Auditory Hallucination Rating Scale (AHRS) will be the primary outcome measure for this study. This survey instrument will be administered at the first recruitment visit, two weeks later at the screening visit, at baseline ( $t_0$ ) on the first day of stimulation, after stimulation on the fifth day of stimulation ( $t_1$ ), and at each of the 8 weekly maintenance sessions ( $t_2, t_3, t_4, t_5, t_6, t_7, t_8, t_9$ ). The primary analyses will focus on longitudinal changes from baseline in the AHRS scores at  $t_1$  and  $t_9$  accounting for the following explanatory variables: treatment regimen, treatment stage (initial daily stimulation vs maintenance weekly stimulation), and the baseline AHRS score as a covariate.

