##### **4.1.2 SECONDARY OUTCOME MEASURES**

We will compare alpha oscillations from resting state EEG recording from the first day ( $t_0$ ) and last day ( $t_1$ ) of the stimulation week. We will also collect EEG data at the maintenance sessions at weeks 1, 3, and 8 ( $t_2, t_4, t_9$ ). We will use these data to analyze alpha frequency activity for derivation of EEG biomarkers. Furthermore, we will estimate

the locations and strengths of the current sources in the brain using source localization techniques based on individual locations of scalp electrodes and anatomical structures.

The Positive and Negative Syndrome Scale (PANSS) and Brief Assessment of Cognition in Schizophrenia (BACS) will also be secondary outcome measures for this study. These measurements will be taken at the first day of stimulation ( $t_0$ ), last day ( $t_1$ ) of stimulation and at the final maintenance stimulation visit ( $t_9$ ). PANSS and BACS scores serve as measures of other positive, negative and general symptoms of schizophrenia (PANSS) or cognition (BACS). The analyses of these secondary measures will focus on longitudinal changes from baseline in the scores at  $t_1$  and  $t_9$  accounting for treatment regimen, treatment stage (initial daily stimulation vs maintenance weekly stimulation), and the baseline AHRS score as a covariate.

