## 7 STUDY PROCEDURES/EVALUATIONS

### 7.1 STUDY SPECIFIC PROCEDURES

During the initial session, researchers will collect demographics. Participant demographics include medical history and medication history. This information is used to confirm inclusion criteria and that no current alcohol and drug abuses or disorder exist.

Several clinical evaluations will be used throughout this study. These assessments are listed below and can be found in the attached documents.

- i. The Structured Clinical Interview for DSM-IV Axis I Disorders (SCID-I) is a semi-structured interview used to diagnosis major Axis I disorders. For this study, the SCID-I (First et al. 2004) will be administered at baseline in order to confirm a diagnosis of Schizophrenia or Schizoaffective Disorder.
- ii. The Columbia Suicide Severity Rating Scale (C-SSRS) is a semi-structured interview designed to assess suicidality. The assessment will be administered at baseline, the first day of stimulation, the fourth maintenance stimulation session, and the final maintenance stimulation session.
- iii. The Auditory Hallucination Rating Scale (AHSRS) is a structured interview, designed to assess different aspects of patient's auditory hallucinations. This assessment has 11 items and is rated on a scale of 0 – 4 based on the responses given by the patient. The AHSRS will be administered at the baseline visit, each screening session, the first day of stimulation, the last day of stimulation, and at each of the maintenance stimulation sessions.
- iv. The Positive and Negative Syndrome Scale (PANSS) is a structured interview used to assess the symptom severity of patients diagnosed with schizophrenia. The PANSS (Kay et al. 1987) focuses on the positive and negative syndromes and their general severity. This scale will be administered at the

first day of stimulation, the last day of stimulation and at the final maintenance stimulation session (week 8).

v. The Brief Assessment of Cognition in Schizophrenia (BACS) will be administered at the first day of stimulation, the last day of stimulation and at the final maintenance stimulation session (week 8) in order to monitor changes in participant cognition. This validated assessment (Keefe et al. 2004, Keefe et al. 2006) contains 6 tests that focus on verbal memory and learning, working memory, motor functioning, attention/processing speed, verbal fluency and reasoning and problem solving.

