### 10.2 STATISTICAL ANALYSIS PLANS

The following statistical considerations and aim-specific analysis plans will be reviewed and updated prior to any data collection. To help ensure reproducibility and objectivity of the results, these *a priori* plans specify details for the main analyses for each specific aim; e.g., details of fitted models and decisions regarding the units and scales of the measurements of interest. The plans include 1) sensitivity analyses performed to assess the robustness of the major results to reasonable perturbations of the assumptions and methods used; 2) exploratory analyses for hypothesis generation; 3) necessary descriptive graphical and tabular methods used to visualize the data, and 4) exploration of relationships among the variables of interest. Following best practices (e.g., [www.CONSORT-statement.org](http://www.CONSORT-statement.org)), all statistical estimates (e.g., variances, means, differences) will be reported along with their 95% confidence intervals (C.I.s). Hypothesis tests that are observed to be not statistically significant will be reported as being inconclusive. (Hypothesis tests that are not statistically significant are entirely inconclusive and no conclusions can be drawn from those tests. Statistical test procedures are incapable of establishing that the null hypothesis is true.) The word “inconclusive” will be used when reporting a test that was not statistically significant. To avoid over-reliance on p-values, the focus of the analyses will be on the point-estimates and interval-estimates of the magnitudes of the population parameters of interest (e.g. treatment effects).

**Plans for Aim 1:** *Evaluate the relative efficacy of the tACS treatment regimen and subsequent maintenance regimen in terms of changes in the mean level of the AHRS score.*

Clinical scores (AHRS, PANS, BACS) will be recorded on nine occasions (t): at baseline immediately before the first stimulation session on day 1 (t0), after the stimulation session ending day 5 (t1), and after each weekly maintenance session (t2, t3, t4, t5, t6, t7, t8, t9). The experimental design is best viewed as a 2-treatment, 4-sequence (SS, SA, AS, AA), 2-period randomized crossover with longitudinally repeated measures during the second period. Equivalently, it can also be viewed as a 2-treatment, 4-sequence, 9-period crossover.

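### On day 5, participants assessed by phone or webex give their t1 AHRS before the fifth session, although t1 is defined as after it

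*Combined protocol and SAP*

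**What the plan says.** Section 7.4.3 (Day 5, Visit 9) offers two routes for the AHRS and PANSS. On the remote route, "If they prefer the phone/webex, the participant will be contacted before coming into the lab and the AHRS" and PANSS are given; arrival, vital signs, EEG and the fifth stimulation all come later. On the other route, "If the participant opted to complete the clinical assessments in person, the AHRS" and PANSS are given at the end of the session. The participant chooses.

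Two sections fix t1 after the stimulation. Section 4.1.1 places the AHRS "after stimulation on the fifth day of stimulation". Section 10.2 places t1 "after the stimulation session ending day 5" and applies this to all three scales: "Clinical scores (AHRS, PANS, BACS) will be recorded on nine occasions".

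Other sections give only the day. The Protocol Summary has the AHRS "at the fifth day of stimulation", section 7.1 lists "the first day of stimulation, the last day of stimulation, and at each of the maintenance stimulation sessions", and section 13.3 also names only the day. For the PANSS, section 4.1.2 names the first day, the last day "of stimulation and at the final maintenance stimulation visit", without saying before or after. The BACS is given at the end of the day 5 session for everyone and is not affected.

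**The concern.** The AHRS is the primary outcome, and the primary model uses only t1 and t9. Under 7.4.3 as written, t1 combines scores taken after four sessions (remote) with scores taken after five (in person). The first hypothesis in the Protocol Summary concerns benefit after five days of stimulation. At t0 and t9 the AHRS has one fixed place in the visit, before stimulation on day 1 and after it at week 8.

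Timing is fully confounded with mode: remote means before, in person means after. The rating is not repeated, so no later analysis can separate the two.

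If session 5 adds benefit that the AHRS registers by the time of rating, (μS − μA) is diluted and (τS − τA) shifts by the same amount in the opposite direction. Section 10.2 puts estimates and intervals ahead of p-values and names (μS − μA) as a parameter of interest, so its meaning at t1 matters even if the joint test survives. Bias between arms is not shown, because the choice of mode is made under blinding.

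**Working it through.** **Text.** A rating finished before the participant travels to the lab cannot also follow that day's stimulation. The day-only sections fit either order, so they settle nothing. No section redefines t1 for remote participants.

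**Inputs from the plan.** Table 2 conditional variances: inter-subject 4.98 (2.66 to 12.35), intra-subject 0.55 (0.30 to 1.37). N = 40, 10 per sequence. Example effect 1.18 (section 10.3). Section 10.3 uses separate tests at α = 0.025 as a surrogate for power; the primary test in 10.2 is a joint F-test at 0.05.

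**Reproducing the plan's power.** For the t1/t9 model with compound symmetry:

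- Total variance v = 4.98 + 0.55 = 5.53; correlation r = 4.98/5.53 = 0.9005.
- Var(μS − μA) = 2v(1 − r²)/20 = 2 × 5.53 × 0.1890/20 = 0.1045, so SE = 0.323.
- SE(τS − τA) = √2 × 0.323 = 0.457.
- Non-central F with 1 and 37 df, α = 0.025, effect 1.18: power 90.0%. At the Table 2 variance limits: 49.7% and 99.4%.

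The plan states 90% [50%, 99%], so the model matches.

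**Effect of the mixture.** Two quantities are assumed, not in the documents: f, the share of the t1 effect already captured before session 5, and p, the share choosing phone or webex. The choice is taken to be unrelated to regimen.

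- Measured t1 effect: d1 = 1.18 × [1 − (1 − f)p]. With f = 0.8 and p = 50%: 1.18 × 0.90 = 1.06.
- In this design the t1 and t9 contrasts are uncorrelated with equal variance, so the joint non-centrality is (d1² + d9²)/0.1045, where d9 is the t9 effect. With d1 = 1.18 and d9 = 0.9: (1.392 + 0.810)/0.1045 = 21.1, power 98.2% (2 and 37 df, α = 0.05).

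| Quantity | p = 0 | 25% | 50% | 100% |
|---|---|---|---|---|
| Measured t1 effect, f = 0.8 | 1.18 | 1.12 | 1.06 | 0.94 |
| Surrogate period 1 test, f = 0.8 | 90.0% | 86.6% | 82.4% | 71.9% |
| Joint test, t9 effect 1.18, f = 0.8 | 99.6% | 99.4% | 99.2% | 98.6% |
| Joint test, t9 effect 0.9, f = 0.8 | 98.2% | 97.6% | 96.7% | 94.4% |
| Joint test, t9 effect 0.9, f = 0.9 | 98.2% | 97.9% | 97.6% | 96.7% |
| Joint test, t9 effect 0, f = 0.8 | 89.0% | 85.5% | 81.3% | 70.9% |
| Joint test, t9 effect 1.18, f = 0.8, upper variance limits | 80.9% | 78.8% | 76.7% | 72.2% |
| Joint test, t9 effect 0.9, f = 0.8, upper variance limits | 70.6% | 67.6% | 64.6% | 58.6% |

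With f = 1 every row stays at its p = 0 value. With f = 0.8, (τS − τA) shifts by 1.18 × 0.2 × p = 0.06, 0.12 or 0.24, at most 0.24/0.457, about half its SE.

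**The case against.** The textual conflict is not in dispute; its weight is.

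- **Size is assumed.** Neither f nor p is in the documents. Entry needs only three hallucinations a week, so some participants may have no episode between session and rating. The AHRS recall window is in an attachment not available here. No loss at all is plausible. This stands.
- **The primary test is robust if benefit lasts.** With f = 0.8 and p = 50%, joint power falls by 0.4 points (t9 effect 1.18) or 1.5 points (t9 effect 0.9), and the estimate shifts by 0.12 against an SE of 0.32. The largest falls need p = 100% with either no t9 effect or the surrogate test. At p = 100% nothing is mixed, though every t1 score still precedes session 5. This stands.
- **The 0.9 scenario rests on one reading of 10.2.** The plan expects a small negative τA because weekly stimulation does less than daily. Improvement is a negative change, so a negative τA with τS near 0 makes the t9 effect larger. With τA = −0.28 (illustrative; t9 effect 1.46), joint power goes from 99.9% to 99.8% even at p = 100%. The point is fair, but it affects only the illustration.
- **The PANSS conflict is narrow.** It rests on one sentence in 10.2 that also puts the PANSS at every maintenance session, contrary to 4.1.2 and 7.1. This stands, so the AHRS carries the point.
- **The remedy could cost as much as the defect.** A later call can be missed, and 10.2 analyses completed data sets only. Losing one participant per sequence (N = 36) gives SE 0.341, joint power 96.9% (t9 effect 0.9) and surrogate power 86.2%. That is close to the f = 0.8 dilution at p = 50% (96.7%) and p = 25% (86.6%) respectively. The fix therefore has to guard against missed calls.

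**Conclusion.** The concern holds. Followed as written, 7.4.3 yields a primary-outcome t1 score that breaks the definition in 4.1.1 and 10.2 for every participant who chooses phone or webex; for the PANSS the breach is of 10.2 only. This rests on the text and needs no assumption.

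The consequence is uncertain and falls mainly on the period 1 estimate. Under the assumed f = 0.8, the 1.18-unit effect would be measured as 1.12 to 0.94 for phone shares of 25% to 100%. The joint test loses little at the Table 2 point estimates if benefit persists to t9, and more at the upper variance limits. With f = 1 there is no loss. The sections should be reconciled, but the conflict does not by itself put the primary test in doubt.

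**What to change.** 1. Reconcile 7.4.3 with 4.1.1 and 10.2 so that every t1 AHRS and PANSS follows session 5.
2. Make the in-person rating at the end of the day 5 visit the default. Keep phone or webex only as a call booked for a fixed window later the same day.
3. State in advance what happens if the call is missed: a short permitted late window, the actual time recorded, and no exclusion under the completed-data rule in 10.2 for that reason alone.
4. Record mode and pre/post-session timing on the CRF.
5. Keep participants already rated before session 5 in the primary analysis, and report the mode and timing split by regimen descriptively. A sensitivity model with a timing indicator is optional; it cannot separate timing from mode.

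The cost is a few sentences and one CRF field, with no added visit or procedure. The downsides are a longer visit or a later call on a day already planned at about 4 hours, and a small risk of missed calls. Keeping a participant with a missed call on t9 alone does not restore the period 1 estimate (SE 0.341 either way), which is why the in-person default and late window matter. Payment on day 5 follows the assessments, so a later call also needs one line on payment.

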
	the EEG data, we will also be collecting ECG data. An sMRI visit will be scheduled between the end of the 5 th day of stimulation, and the first maintenance stimulation session.
Objectives	
Our primary objective is to conduct a randomized clinical trial to investigate the ability of tACS to renormalize pathological alpha oscillations in dl-PFC of patients with schizophrenia and schizoaffective disorder and experiencing auditory hallucinations by comparing sham and active treatment regimens in terms of longitudinal changes in AHRS scores and other measures. We also aim to evaluate the ability of an 8-week maintenance regimen to prolong the duration of stimulation-induced clinical benefits in terms of longitudinal changes in AHRS scores and other measures. We hypothesize that (1) tACS reduces auditory hallucination symptoms after 5 consecutive days of daily stimulation and (2) repeat application of tACS during a follow-up maintenance regimen extends the duration of the clinical benefits of the initial stimulation.
 
Our secondary objective is to collect further data demonstrating the value of oscillations and connectivity measures derived from EEG data as novel biomarkers in the treatment of medication refractory auditory hallucinations in schizophrenia with transcranial current stimulation. To reach this objective, we will test the working hypothesis that (1) baseline impairment in EEG oscillations and connectivity predicts treatment success, and (2) changes in these markers correlate with improvement of clinical symptom presentation as measured by the AHRS, PANSS (Attachment 5), and BACS (Attachment 6). We will collect data to support our working hypothesis by measuring whole-head EEG data with individual locations of scalp electrodes and structural MRI from all patients in our study (40 patients from Aim 1) before and immediately after the five day course of stimulation and at each maintenance stimulation visits for weeks 1, 3 and 8.

End date	December 2020

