#### 7.4.5 MAINTENANCE SESSIONS

##### **Maintenance Stimulation Session Week 1 (Visit 11)**

Upon participant arrival, vital signs will be taken and documented. Female participants will complete a urine pregnancy test to rule-out pregnancy. An EEG will then be administered, with ECG data also being collected at this time. The EEG recording will include resting state data along with an auditory task, and the EEG Questionnaire will be administered. The participant will receive 40-minutes of sham or 10 Hz tACS (as per the randomization) while sitting quietly with their eyes open. The stimulation session will be followed by the stimulation adverse effects questionnaire. The AHRS and HPSVQ will then be administered to assess severity of auditory hallucinations. Participants will be paid at the conclusion of this study visit, and the next study visit will be scheduled for the following week.

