**Plans for Aim 2.** *Evaluate the relative efficacy of the tACS treatment regimen and subsequent maintenance regimen in terms of changes in the mean levels of the PANSS score and the BACS score.*

We anticipate that the strategy and methods used for the analyses of AHRS scores in Aim 1 will also be appropriate for the analysis of PANSS and BACS scores for Aim 2.

**Plans for Aim 3.** *Evaluate the effects of the tACS treatment regimen and subsequent maintenance regimen in terms of changes in EEG alpha frequency power levels.*

We anticipate that the strategy and methods used for the analyses for Aim 1 will also be appropriate for the analyses in Aim 3 of changes in alpha band power calculated from EEG recordings. Graphical descriptive statistical methods will be used to visualize and summarize the temporal trajectories of the scores and alpha band power. Scores of clinical assessments and EEG recordings at other occasions of the maintenance sessions may be explored for the purpose of generating hypotheses.

**Plans for early discontinuation:** In the event of a participant discontinuing participation prior to completion of the study sessions, the participant's data set will not be included in analysis. Only completed data sets will be included in analysis.

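### Every EEG is described as pre-stimulation, so the t1 EEG follows four of the five initial sessions and the t2 EEG precedes all maintenance; the objective and the coding carried over to Aim 3 do not reflect this

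*Combined protocol and SAP*

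**What the plan says.** The Protocol Summary (Objectives) places EEG "before and immediately after the five day course of stimulation and at each maintenance stimulation visits for weeks 1, 3 and 8". The initial course is five sessions: "the enrolled participants will have 5, daily, 40-minute stimulation sessions".

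The visit procedures give a different order. On day 5 (section 7.4.3) the EEG comes first: "the EEG Questionnaire will be administered. The participant will receive 40-minutes of sham or 10 Hz tACS (as per the initial randomization". Maintenance week 1 (section 7.4.5) has the same sequence: "the EEG Questionnaire will be administered. The participant will receive 40-minutes of sham or 10 Hz tACS (as per the randomization". Weeks 2 and 3 (7.4.5) and week 8 (7.4.6) follow it too. The baseline EEG on day 1 also precedes stimulation. No post-session EEG is described anywhere.

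Section 10.2 defines t1 for the clinical scores as "after the stimulation session ending day 5", and the later occasions as "and after each weekly maintenance session". Section 4.1.2 uses the labels t0 and t1 for EEG and then adds t2, t4 and t9: "We will also collect EEG data at the maintenance sessions at weeks 1, 3, and 8". It does not say whether these are before or after the session. Aim 3 has no model of its own; section 10.2 anticipates that the Aim 1 strategy "will also be appropriate for the analyses in Aim 3 of changes in alpha band power calculated from EEG recordings".

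**The concern.** One set of labels covers two measurement schedules. An EEG labelled t1 would naturally be reported as the state after the full course, when it is the state about a day after the fourth session.

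At t2 the mismatch is one of kind. Table 1 separates SA from SS, and AA from AS, by the maintenance regimen. When the week-1 maintenance EEG is recorded, no maintenance session has taken place, so the two members of each pair have the same treatment history. A model that assigns a maintenance effect there dilutes that effect and disturbs the other estimates.

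The hypothesis that EEG change tracks symptom change (section 10.1) is also touched. At maintenance visits the AHRS is rated after the session and the EEG is recorded before it, so pairs sharing a label differ by one session.

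**Working it through.** **Sessions completed before each EEG.** On day 5 this is 5 - 1 = 4. At maintenance week w it is w - 1.

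| EEG | Procedure | Completed before EEG | Implied if the label has its clinical-score meaning |
|---|---|---|---|
| t1 | 7.4.3, day 5 | 4 of 5 initial | 5 |
| t2 | 7.4.5, week 1 | 0 of 8 maintenance | 1 |
| t3 | 7.4.5, week 2 | 1 of 8 | 2 |
| t4 | 7.4.5, week 3 | 2 of 8 | 3 |
| t9 | 7.4.6, week 8 | 7 of 8 | 8 |

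Week 2 is in the visit procedure but not in the lists of weeks 1, 3 and 8 (Protocol Summary, 4.1.2, 13.3).

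**Check of the model set-up.** The plan states no EEG figure. Its nearest figure is the AHRS power in section 10.3: 90% [50%, 99%] at a difference of 1.18 with size 0.025. With 10 participants per sequence, compound symmetry and the Table 2 conditional components 4.98 (inter-subject) and 0.55 (intra-subject), the standard error of the period-1 contrast in the {t1, t9} fit is 0.3233. The non-centrality is (1.18/0.3233)² = 13.3, which gives power of 90%. The interval limits of the components give 50% and 99%. The plan's figure is reproduced and is not in dispute.

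**What Table 1 implies at t2.** SA minus SS and AA minus AS both equal (m_A + τ_A) - (m_S + τ_S). For an EEG taken before the first maintenance session, both true differences are zero.

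**Illustration.** Assumptions: a true active-minus-sham effect of -1 unit in both periods, except no maintenance effect at t2; carryover modelled at t2 to t4; 10 per sequence; baseline covariate omitted; correlation 4.98/(4.98 + 0.55) = 0.90 borrowed from AHRS, because the documents give no EEG variance. The expected estimates are b = (Σ X'V⁻¹X)⁻¹ Σ X'V⁻¹m, with X coded as in Table 1, m the true means and V compound-symmetric.

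First and second regimens are fully crossed in equal numbers, so the period-2 estimate is the plain average over the k maintenance EEGs used: -(k - 1)/k.

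| EEG occasions fitted | Period-2 effect | Period-1 effect | Shift in λ |
|---|---|---|---|
| t1, t2, t4, t9 | -2/3 = -0.67 | -0.84 | +0.24 |
| t1, t2, t3, t4, t9 | -3/4 = -0.75 | -0.88 | +0.16 |
| t1, t2, t9 | -1/2 = -0.50 | -0.77 | +0.49 |

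The period-2 figures do not depend on the correlation; the other two columns do. They shift because Table 1 gives each regimen one level across t2 to t9, apart from λ. The missing effect at t2 is therefore partly read as carryover, and it reaches period 1 through the within-participant correlation. If t2 is given two means of its own, one per week-1 regimen, the fits that include t4 return -1 in both periods and the true λ.

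**The case against.** Pre-session EEG at every visit is a sound design. Baseline is pre-session too, so change from baseline compares like with like and avoids the acute after-effect of a session just given. Section 4.1.2 and the visit procedures agree with each other; the direct contradiction is one phrase in the Protocol Summary. Section 10.2 defines its occasions for clinical scores, Table 1 and the carryover fit are written for AHRS, and Aim 3 says only that the Aim 1 approach is anticipated to be suitable. EEG at other maintenance occasions is described as hypothesis-generating.

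All of that stands, and it limits the point. It does not remove it: the labels are reused for EEG without redefinition, and nothing says the t2 EEG is to be handled differently.

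Some stronger readings are not supported:

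- A reader might infer an EEG at every maintenance visit. Section 7.3.2 says so, but the weeks 4-7 procedure has none.
- A reader might call the SA group unstimulated at t2. Sham includes 20 seconds of 10 Hz tACS (section 4.2); the accurate statement is that SA has had no active regimen.
- A reader might take all EEG-symptom pairs as mismatched. On day 5, participants who choose phone or webex are rated before the session, at the same session count as their EEG.

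**Conclusion.** The timing finding rests on the documents alone: the t1 EEG follows 4 of 5 initial sessions, against the Protocol Summary, and the t2, t4 and t9 EEGs follow 0, 2 and 7 of 8 maintenance sessions.

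The modelling finding is conditional. If the carryover model is applied to EEG with Table 1 coding, the maintenance effect shrinks by between one quarter and one half in the cases shown, and the period-1 and carryover estimates move as well. These sizes are illustrative: they assume a constant effect from the first maintenance session onward, and the last two also assume the borrowed correlation.

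A reader might infer that the main Aim 3 comparison or the trial's primary result is biased by the t2 coding. The documents do not support that. The {t1, t9} strategy does not contain t2 and is affected only by the missing last session at each time, and EEG timing does not enter the primary AHRS analysis. This is an inexpensive correction to a secondary aim that is worth making.

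**What to change.** - Keep the EEG before the session at all visits, so that it matches baseline. Moving only the day-5 EEG to after the session would mix an acute after-effect into t1 alone.
- In the Protocol Summary, section 4.1.2 and the Aim 3 plan, define EEG occasions separately from clinical-score occasions: t1 is after four daily sessions and before the fifth; t2 is after the initial week and before any maintenance; t4 and t9 are after two and seven maintenance sessions.
- In the Aim 3 carryover analysis, code t2 by week-1 treatment only, with no maintenance term, and use it to measure how long the week-1 alpha change persists.
- In the EEG-symptom analysis, state that maintenance EEG precedes the session and AHRS follows it, and record which day-5 ratings were made before the session.
- Reconcile section 7.3.2 (EEG at each maintenance session) and the week-2 procedure in 7.4.5 with the lists of weeks 1, 3 and 8.

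The cost is protocol and SAP wording and the coding of one visit, with no change to the order of procedures within a visit. The claim to measure EEG immediately after the five-day course is given up. With t2 coded separately, λ for EEG rests on fewer recordings (t4 alone if EEG is kept to weeks 1, 3 and 8), so it will be less precise.
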